The advent of targeted therapies has markedly shifted the paradigm in the treatment of non-small cell lung cancer (NSCLC), particularly for patients with specific genetic alterations such as ALK rearrangements. A small retrospective study of the first-generation ALK-TKI crizotinib in the neoadjuvant setting included 11 ALK-positive, N2 NSCLC patients who received oral crizotinib (250mg twice daily) for a median duration of 30 days (range 28-120 days). This study demonstrated a 91.0% R0 resection rate with 18.2% (2 cases) achieving pathological complete response post-treatment. The SAKULA study, a phase II multicenter single-arm trial, assessed the efficacy and safety of the second-generation ALK-TKI ceritinib in resectable ALK-positive NSCLC. The study enrolled 7 cases all at stage IIIA (N2), and treated with oral ceritinib (750mg twice daily) as neoadjuvant therapy. The primary endpoint of major pathological response (MPR) was 57% (95% CI: 18-90), with 2 cases achieving complete remission (29%). NAUTIKA1, a phase II trial, investigated the efficacy of alectinib as neoadjuvant therapy for 8 weeks in patients with resectable stage II, IIIA, and IIIB NSCLC, followed by surgery, 4 cycles of adjuvant chemotherapy, and 2 years of alectinib adjuvant treatment. Among 9 patients, 6 achieved a major pathological response (MPR), resulting in an MPR rate of 66.7% (95%CI, 29.9%-92.5%), with a pathological complete response (pCR) rate of 33.3%. Eight patients underwent R0 resection. These results indicate the feasibility and potential efficacy of ALK-TKIs in improving surgical outcomes and reducing the tumor burden before surgery, making it a promising neoadjuvant treatment option for this patient population.

This study seeks to assess the feasibility of lorlatinib as neoadjuvant therapy for patients with resectable, stage IB-IIIB ALK+ lung adenocarcinoma. Given lorlatinib's advanced efficacy in targeting ALK-positive tumors, including its activity against resistant mutations and its proficiency in managing CNS metastases, this study aims to evaluate the efficacy and safety of lorlatinib as neoadjuvant therapy in patients, focusing on improvements in pathological response, surgical outcomes, prolonged survival, and safety/tolerability.

[figure not shown]
	Phase: Phase II
--	------------------------

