## **3. STUDY DESIGN**

### **Figure 1. Study Design**

### 3.1 Study design

This protocol delineates a Phase II, open-label, single-arm, prospective, multi-center study designed to evaluate the efficacy and safety of lorlatinib as a neoadjuvant therapy in patients with resectable ALK-positive non-small cell lung cancer (NSCLC). [Figure 1]

Eligible participants include male and female subjects aged  $\geq 18$  years, diagnosed with clinical stage IB, II, IIIA, or selected IIIB (including T4N2, as per the American Joint Committee on Cancer [AJCC] 8th edition) NSCLC, as assessed by positron emission tomography/computed tomography (PET/CT), or through computed tomography (CT), abdominal ultrasound, cranial MRI/CT, and bone scintigraphy. Enrollment criteria mandate that all tumors must test positive for ALK rearrangement, verified through Ventana ALK (D5F3), next-generation sequencing (NGS), etc. testing methods. All tumors will be of histo- and/or cytopathology consistent with NSCLC. Performance status (ECOG) 0-1 at enrolment, with no deterioration over the previous 2 weeks prior to baseline or day of first dosing of lorlatinib.

Upon meeting eligibility criteria, patients will be registered to receive oral lorlatinib at a dose of 100mg once daily (qd) for a period of 6-8 weeks, assessment will be conducted after 4 weeks, as determined by the attending clinicians based on the best clinical

practice. The duration of neoadjuvant therapy has been designed to optimize treatment efficacy while ensuring the feasibility of subsequent surgical resection.

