### 4.1 Inclusion Criteria

Subjects must meet all the following inclusion criteria to be eligible for enrollment into the study:

- Male or female subjects who are  $\geq 18$  years of age
- Histologically or cytologically documented non-squamous surgically resectable stage IB, II, IIIA or selected IIIB NSCLC (including T4N2, per AJCC 8th edition)
- Clinical stage IB, II, IIIA or selected IIIB assessed PET/CT that can be resected
- Documented ALK-rearrangement positive (assessed by a local laboratory)
- Performance status (ECOG) 0-1 at enrolment, with no deterioration over the previous 2 weeks prior to baseline or day of first dosing of lorlatinib
- Hematology, liver and kidney function are adequate for induction therapy.
  - Adequate Bone Marrow Function, including:
    - a. Absolute Neutrophil Count (ANC)  $\geq 1,500/\text{mm}^3$  or  $\geq 1.5 \times 10^9/\text{L}$ ;
    - b. Platelets  $\geq 100,000/\text{mm}^3$  or  $\geq 100 \times 10^9/\text{L}$ ;
    - c. Hemoglobin  $\geq 9 \text{ g/dL}$ .
  - Adequate Pancreatic Function, including:
    - a. Serum total amylase  $\leq 1.5 \times$  upper limit of normal (ULN)\*;

b. Serum lipase  $\leq 1.5 \times$  ULN.

\*if total amylase  $> 1.5 \times$  ULN, but pancreatic amylase is within the ULN, then patient may be enrolled.

- Adequate Renal Function, including:

a. Serum creatinine  $\leq 1.5 \times$  ULN or estimated creatinine clearance  $\geq 60$  mL/min as calculated using the method standard for the institution.

- Adequate Liver Function, including:

a. Total serum bilirubin  $\leq 1.5 \times$  ULN;

b. Aspartate Aminotransferase (AST) and Alanine Aminotransferase (ALT)  $\leq 2.5 \times$  ULN ( $\leq 5.0 \times$  ULN in case of liver metastases).

- Cardiopulmonary function suitable for surgical treatment (ECG, echocardiography, pulmonary function or blood gas analysis).
- Be willing and able to provide written informed consent for the trial prior to any study specific procedures. The subject must also provide consent for correlative translational study.
- Female participants of childbearing potential must agree to use acceptable methods of contraception
- Male patients must be willing to use barrier contraception.
- Serum pregnancy test (for females of childbearing potential) negative at screening. Female patients of non-childbearing potential must meet at least 1 of the following criteria:

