#### **6.4.8 Subject Withdrawal**

A subject may withdraw from treatment at any time at their own request, or they may be withdrawn at any time at the discretion of the investigator for safety, behavioral, or administrative reasons. Reasons for withdrawal include, but are not limited to the following:

- Progressive disease as defined by RECIST version 1.1 (as determined by investigator assessment) and judged by investigator that the patient no longer derives clinical benefit from study treatment;
- New systemic anticancer therapy instituted;
- Unacceptable toxicity;
- Global deterioration of health-related symptoms;
- Study non-compliance;
- Subject becomes pregnant;
- Subject withdraws from treatment;
- Lost to follow-up;
- Die;
- Study termination by investigator.

If subjects require more than 2 consecutive weeks of dose interruption, a discussion should be made with the investigator.

If a subject does not return for a scheduled visit, every effort should be made to contact the subject. The investigator should inquire about the reason for withdrawal, request that the subject return all unused investigational product(s), request the subject returns for a final visit if applicable, and follow up with the subject regarding any unresolved AEs.

If the subject withdraws from the study and also withdraws consent for disclosure of future information, no further evaluations should be performed and no additional data should be collected. The investigator may retain and continue to use any data collected before withdrawal of consent.

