##### *Full-Analysis-Set (FAS) Population*

The FAS will include all participants who are enrolled. The FAS will be the primary population for evaluating all efficacy endpoints and participant characteristics.

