#### **9.2.4 Definitions of Secondary Efficacy Endpoints**

Major pathologic response (MPR): defined as  $\leq 10\%$  residual viable tumor cells histologically detected in the resected primary tumor and all resected lymph nodes after surgery.

Objective response rate (ORR): defined as a complete response or a partial response at the presurgical radiologic evaluation, based on the investigator's assessment according to RECIST v1.1;

Surgical outcomes and intraoperative events:

Rate of lymph node downstaging: It is defined as the proportion of patients who have completed the neoadjuvant lorlatinib treatment before surgery and have achieved a N stage downing of the tumor as confirmed by CT evaluation after 6 weeks in all patients who have completed the treatment.

Unanticipated delays to surgery: It is defined as the proportion of patients who have unanticipated delays to surgery  $> 6$  weeks after completion of neoadjuvant treatment.

Surgical complication rate: It is defined as the proportion of patients who have completed the surgery after neoadjuvant lorlatinib treatment.

Safety and tolerability per NCI-CTCAE v5.0.

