#### **9.2.5 Analysis of Secondary Endpoints**

All analyses will be performed using the FAS.

Objective Response on each treatment arm will be summarized based on the investigator's assessment. The number and percent of subjects achieving objective response (CR or PR) will be summarized along with corresponding 2-sided 95% CI using the binomial distribution.

MPR rate refers to the proportion of patients  $\leq 10\%$  residual viable tumor cells histologically detected in the resected primary tumor and all resected lymph nodes after surgery assessed by the investigator.

Descriptive data analyses will be conducted for both primary and secondary objectives. Categorical variables will be summarized including the number of non-missing observations, the frequency of the observed endpoint as well as the observed proportion. Continuous variables will be summarized including the number of non-missing observations, mean (Standard Deviation [SD]), median, Q1, Q3, and the minimum/maximum.

- MPR, and ORR will be summarized using frequency counts and percentages with 95% CIs.
- Continuous variables in surgical outcomes will be summarized using median and range.

Categorical variables in surgical outcomes, safety and tolerability will be summarized using frequency counts and percentages.

Descriptive statistics will be used to summarize subject characteristics, study conduct, subject disposition, treatment administration/compliance, and safety parameters.

Data will also be displayed graphically, where appropriate.

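### The lymph-node downstaging rate keeps baseline node-negative patients in its denominator, and its completer base contradicts the protocol's FAS rule

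*Protocol*

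**What the plan says.** Section 9.2.4 of the Protocol counts patients who finished neoadjuvant lorlatinib and whose N stage fell, "as confirmed by CT evaluation after 6 weeks in all patients who have completed the treatment". The denominator is thus stated, and it is treatment completers of any nodal status. The endpoint lists in the Synopsis and in section 2.2 name the rate without qualifying it.

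Eligibility is by overall stage. Section 4.1 asks for "Histologically or cytologically documented non-squamous surgically resectable stage IB, II, IIIA or selected IIIB NSCLC", and section 3.1 describes participants "diagnosed with clinical stage IB, II, IIIA, or selected IIIB". Neither section requires involved nodes, and no exclusion criterion removes node-negative patients.

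On populations, section 9.2.1 defines the FAS as everyone enrolled and says: "The FAS will be the primary population for evaluating all efficacy endpoints and participant characteristics". Section 9.2.5, on the secondary endpoints, says: "All analyses will be performed using the FAS". Neither makes an exception for downstaging.

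**The concern.** A downstaging rate is meant to show how often involved nodes respond. A patient who starts at N0 has no lower N category to reach, so that patient's result is fixed before treatment begins. Counting such patients as not downstaged makes the percentage depend on the nodal mix of the sample as well as on the effect of the drug. In a trial of 25, that mix can shift appreciably by chance.

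The second problem is separate. Section 9.2.4 uses completers, while 9.2.1 and 9.2.5 use all enrolled patients. Two analysts following different sections would report different percentages from the same data. Moving to the FAS alone would not cure the first problem, because the FAS also contains the N0 patients.

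**Working it through.** **Inputs from the Protocol.** Denominator: all treatment completers (9.2.4). Eligible stages: IB to selected IIIB, no nodal criterion (3.1, 4.1). Planned enrolment: 25 (9.1). Analysis set for secondary endpoints: FAS (9.2.1, 9.2.5). The Protocol states no expected downstaging rate, so there is no figure of its own to reproduce.

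**Inputs not in the Protocol.** The share *f* of completers who are N0 at baseline, and the downstaging rate *q* among node-positive completers. Both are assumed below.

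**Step 1: what the rule reports.** With *n* completers, *n*(1 − *f*) are node-positive and *q* × *n*(1 − *f*) of them are downstaged. No N0 patient can be added to the numerator. Hence

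reported rate = *q* × *n*(1 − *f*) / *n* = (1 − *f*) × *q*.

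Since *q* cannot exceed 1, the ceiling is 1 − *f*. If 40% of completers are N0, the rule cannot report more than 60%, even if every node-positive patient is downstaged.

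**Step 2: illustration with 25 completers and *q* = 60%.**

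| Assumed N0 share | As written | Node-positive completers |
|---|---|---|
| 0% | 15/25 = 60% | 15/25 = 60% |
| 20% | 12/25 = 48% | 12/20 = 60% |
| 40% | 9/25 = 36% | 9/15 = 60% |
| 60% | 6/25 = 24% | 6/10 = 60% |

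In the 40% row, the exact 95% intervals are 18.0% to 57.5% as written and 32.3% to 83.7% when restricted. Over N0 shares of 20% to 60% and *q* of 40% to 80%, the rule reports 16% to 64%, where the node-positive rate is 40% to 80%.

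**Step 3: completers against the FAS, taken alone.** Suppose 25 are enrolled, none is N0, 5 stop early without a downstaging result, and 12 of the remaining 20 are downstaged. Section 9.2.4 gives 12/20 = 60%; section 9.2.5 gives 12/25 = 48%. These counts are hypothetical. They show only that the two sections lead to different answers, and that this difference runs opposite to the N0 dilution.

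**Step 4: precision after restriction.** One patient moves the rate by 100/25 = 4.0 percentage points with 25 in the denominator, 100/20 = 5.0 with 20, 100/15 = 6.7 with 15 and 100/10 = 10.0 with 10.

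**The case against.** The best defence is one of weight. The endpoint is one of several secondary surgical outcomes. It carries no hypothesis and no threshold, and section 9.2.5 plans confidence intervals for MPR and ORR but only counts and percentages for categorical surgical outcomes. If baseline N stage appears among the reported patient characteristics, a reader could largely rebuild the node-positive rate. A proportion over all completers is also not a miscalculation; it answers a less useful question. Section 9 further allows the SAP to modify the plan. All of this limits the importance of the point. It does not remove it, because the Protocol has already fixed the denominator, and an SAP that follows it carries the fault forward.

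Three stronger readings are tempting, and the Protocol does not support them.

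- *The reported rate must be too low overall.* The dilution lowers it relative to node-positive completers. Relative to node-positive patients in the FAS, the completer restriction can push the other way, and the Protocol gives neither the N0 share nor the non-completion share. The net direction is unknown.
- *The rate cannot be set against earlier neoadjuvant ALK studies.* The Background describes one that "included 11 ALK-positive, N2 NSCLC patients" and says of another: "The study enrolled 7 cases all at stage IIIA (N2". But it reports no downstaging rate for any cited study, and no comparison on this endpoint is planned.
- *Using completers discards patients because they progressed.* Section 6.4.8 lists "Progressive disease as defined by RECIST version 1.1" as a reason for withdrawal, but adds that the investigator must also judge that clinical benefit has been lost. Section 5.1 does not name progression among its criteria for ending lorlatinib. Removal related to outcome is possible; the text does not make it automatic.

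**Conclusion.** The point stands as a correction to a definition. As written, the rate equals (1 − N0 share) times the rate in node-positive completers and is capped at 1 − N0 share. That follows from the stated denominator and the absence of a nodal criterion, and it needs no assumed value. The size does: 36% against 60% rests on an assumed 10 N0 patients among 25 completers with 9 downstaged, and the gap is zero if no N0 patient is enrolled.

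The clash between the completer base and the FAS rule is a plain contradiction in the text, whatever its numerical effect.

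The change should be made before analysis, but the impact is limited to one descriptive secondary endpoint. The pCR decision rule, its error rates and the sample size do not use this endpoint.

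**What to change.** In section 9.2.4, define the rate as the proportion of FAS patients with clinical N1 or higher at baseline whose N stage is lower on the post-treatment CT. State that patients without a post-treatment nodal evaluation count as not downstaged. Show the rate among node-positive completers alongside. This also settles the conflict with 9.2.1 and 9.2.5.

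The CT time point can stay as stated, or be aligned explicitly with the end-of-neoadjuvant imaging already in Table 1. The point made here does not depend on that choice.

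No new data are needed: TNM staging is done at screening and imaging is scheduled before surgery. The costs are a short rewording and a smaller denominator. If 40% of 25 patients were N0, 15 would remain and each would move the rate by 6.7 rather than 4.0 percentage points. Little is lost by this, since N0 patients carry no information on downstaging. Counting unevaluated patients as not downstaged is a conservative choice, and the completer rate shown beside it lets readers see its effect.

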### **Secondary Efficacy Endpoints:**

[figure not shown]
- Major pathologic response (MPR) assessed by investigator (defined as no more than 10% residual viable tumor cells in the surgical specimen).
- Objective response rate (ORR) per RECIST 1.1 , investigator-assessed;
- Surgical outcomes and intraoperative events
- Rate of lymph node downstaging;
- Unanticipated delays to surgery;
- Surgical complication rate;
- Safety and tolerability per NCI-CTCAE v5.0.

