13. Adverse event assessment includes tumor-related, treatment-related and unrelated signs and symptoms. The reporting period for non-serious AEs starts from the time the subject has taken the first dose of study treatment and ends at last subject visit or upon initiation of a subsequent anticancer treatment, whichever occurs first. The reporting period for serious AEs starts once a subject provides informed consent and ends 28 days after the last dose of study treatment irrespective of the start of

any subsequent anticancer treatment. Subjects must be followed for AEs at Post-Treatment Follow-up Visit at least 28 (and no more than 35) days after the end of treatment, or until all drug-related toxicities have resolved or are deemed irreversible, whichever is later. The National Cancer Institute Common Terminology Criteria for Adverse Events, Version 5.0 (CTCAE v5.0) will be used to grade AE severity.

14. Tumor assessments will include: PET/CT, or through computed tomography (CT), abdominal ultrasound, cranial MRI/CT, and bone scintigraphy at screening, in order to determine the accurate TNM staging. Physical examination for peripheral adenopathy or skin/subcutaneous nodules representing target measurable (by caliper) disease, if any are present.. Imaging serves also as safety assessment to monitor/exclude pulmonary toxicity. Chest X-ray will be performed on the first postoperative day to assess the surgical outcome and any procedural events. A chest X-ray will be conducted one month postoperatively to evaluate postoperative pulmonary recovery, including the presence of pleural effusion.
15. Subject Status Follow-up for Survival: Repeat tumor assessments are suggested to be done approximately every 4 weeks from the date of CT/MRI at the end of study treatment. Telephone contact approximately every cycle from post treatment follow-up visit to obtain regular follow-up is recommended. The information collected for subsequent therapies should include enumeration of the post-study treatment, including drugs administered, and date of initiation and discontinuation of each drug; and will be recorded in the CRF.

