## **8.1 Reporting Period**

For SAEs, the active reporting period to the investigator or its designated representative begins from the time that the subject provides informed consent, which is obtained prior to the subject's participation in the study, i.e., prior to undergoing any study-related procedures and/or receiving investigational product, through and including 28 calendar days after the last administration of the investigational product regardless of the start of any subsequent cancer therapy. SAE should be reported via the CRF in the active reporting period. Following the active safety reporting period, other SAEs of which the investigator becomes aware should be reported to drug provider, unless the SAE is attributed by the investigator to complications of either the underlying malignancy or any subsequent anti-cancer therapy or to the patient's participation in a subsequent clinical study.

Non-serious adverse events should be recorded on the CRF from the time the subject has taken at least one dose of study treatment through last subject visit.

If a subject begins a new anticancer therapy, the AE reporting period for non-serious AEs ends at the time the new treatment is started.

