### **9.3 Safety Analysis**

The SAT Population will be the primary population for evaluating safety.

All subjects who receive at least one dose of study medication will be included in the summaries and listings of safety data. The overall safety profile and toleration of lorlatinib will be characterized by type, frequency, severity (as graded by CTCAE v5.0), timing and relationship of study treatment of AEs and laboratory abnormalities, by

treatment arm, as appropriate.

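### The surgical complication rate is defined as a surgery-completion rate, and no complication enters it

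*Protocol*

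**What the plan says.** The synopsis and section 2.2 of the protocol list "Surgical complication rate" among the secondary endpoints without defining it. The only definition is in section 9.2.4: "Surgical complication rate: It is defined as the proportion of patients who have completed the surgery after neoadjuvant lorlatinib treatment".

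Section 9.2.5 sets the population for secondary endpoints, "All analyses will be performed using the FAS", and section 9.2.1 makes the FAS everyone enrolled. For the summary, section 9.2.5 says only: "Categorical variables in surgical outcomes, safety and tolerability will be summarized using frequency counts and percentages". Safety has its own population in section 9.3: "The SAT Population will be the primary population for evaluating safety".

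On data capture, Table 1 schedules adverse event assessment at the surgery-complete visit and at the final visit 1 month after surgery. Section 3.1 allows surgery up to 6 weeks after lorlatinib ends. For serious events, Table 1 footnote 13 states: "The reporting period for serious AEs starts once a subject provides informed consent and ends 28 days after the last dose of study treatment". Section 8.1 sets the same limit, adds "SAE should be reported via the CRF in the active reporting period", and for the time afterwards says that "other SAEs of which the investigator becomes aware should be reported to drug provider", with exceptions for events attributed to the malignancy, to later anticancer therapy or to a later trial.

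**The concern.** The label promises a safety outcome and the definition delivers a feasibility outcome. A surgery-completion rate depends on how many patients are operated on. It carries no information on how many of them have a complication, and a higher value is good news, whereas a higher complication rate is bad news.

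Surgical outcomes and safety are stated secondary objectives of this neoadjuvant trial. If the definition is copied into the analysis, a named endpoint would be reported with a figure that does not measure it. If the analyst departs from the definition, the event, the time window and the denominator would all have to be chosen later, possibly with the results of an open-label, single-arm trial in view.

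**Working it through.** The protocol gives no figure for this endpoint, so there is none to reproduce. The check is a comparison of the text, followed by an illustration.

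**Text**

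- Synopsis and section 2.2: name the endpoint, no definition.
- Section 9.2.4: patients who completed surgery. No complication event, no grade, no time window.
- Section 9.2.5: the FAS, with counts and percentages. Confidence intervals are planned only for MPR and ORR.
- Section 9.2.4, neighbouring entry on unanticipated delays to surgery: names its event, a delay of more than 6 weeks. The section therefore does specify events, and the gap is particular to this endpoint.

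**Illustration**

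N = 25 is from the protocol. The numbers operated on and the numbers with a complication are assumptions.

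- Rate as written = operated / FAS.
- Complication rate among operated patients = patients with a complication / operated.
- Complication rate on the FAS = patients with a complication / FAS.

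| Operated | With complication | As written | Complications / operated | Complications / FAS |
|---|---|---|---|---|
| 24 | 0 | 24/25 = 96% | 0/24 = 0% | 0/25 = 0% |
| 24 | 3 | 24/25 = 96% | 3/24 = 12.5% | 3/25 = 12% |
| 24 | 12 | 24/25 = 96% | 12/24 = 50% | 12/25 = 48% |
| 20 | 3 | 20/25 = 80% | 3/20 = 15% | 3/25 = 12% |

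In the first three rows the written rate stays fixed while complications go from none to half of the operated patients. Between the second and fourth rows the number of complications is the same, yet the written rate falls by 96 − 80 = 16 percentage points because fewer patients are operated on. If the literal definition is instead applied to operated patients only, it is 24/24 or 20/20, that is 100% in every row.

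**Reporting periods**

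- SAE reporting under section 8.1 and footnote 13 ends on day 28 after the last dose.
- With surgery at the end of the 6 weeks allowed in section 3.1, surgery falls on day 42. Taking 1 month as 30 days, the final visit is on day 42 + 30 = 72.
- The final visit can therefore fall 72 − 28 = 44 days after the stated period closes.

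**Neighbouring denominator**

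The nodal downstaging rate in section 9.2.4 is taken over patients who completed treatment, while section 9.2.5 puts all secondary analyses on the FAS. The two differ whenever an enrolled patient does not complete treatment. The size of the difference cannot be derived from the protocol.

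**The case against.** The strongest reply is that the label makes the intent plain. An analyst would have to disregard it to report 96% as a complication rate, so the practical defect is one missing numerator in a descriptive secondary endpoint that has no test and no planned interval. Complications are also picked up elsewhere: adverse events are assessed at surgery and 1 month later, chest X-rays are taken on the first postoperative day and at 1 month, and section 9.3 summarises adverse events by CTCAE grade. All of this stands, and it limits the consequences. It does not repair the definition. The intended event, window and denominator cannot be recovered from the text, and a denominator of operated patients would itself depart from the FAS rule. The counts in the illustration are indeed assumed.

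On the SAE period, section 3.1 promises safety follow-up to 1 month after surgery, and section 8.7 has the investigator record in the CRF any SAE linked to study procedures, without a 28-day limit there. These passages soften the point, and nothing here shows that serious complications would be lost. The 28-day limit in section 8.1 and footnote 13 still does not match the schedule. Day 72 applies to surgery within the 6 weeks; delayed surgery would move the visit later.

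On downstaging, a specific denominator can be read as overriding a general sentence. That is reasonable, but the protocol does not say so, and the point is minor.

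Either denominator for complications can be defended. The operated-patient version is preferred because only those patients are at risk of a surgical complication.

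**Conclusion.** The concern holds. The only definition of the surgical complication rate describes surgery completion, and no complication is defined for this endpoint anywhere in the protocol. This is an error in what the protocol states, not a detail left to the SAP. It should be fixed.

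The size depends on counts not yet known. Under the assumed 24 of 25 operated on, the written 96% would stand beside a complication rate anywhere from 0% to 50% of operated patients in the cases shown. The consequence is confined to one descriptive secondary endpoint. The pCR test and the sample size of 25 are unaffected, and surgical safety data are still planned through other routes. The SAE reporting period and the downstaging denominator are secondary points to reconcile.

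**What to change.** 1. Replace the definition in section 9.2.4: number of patients with at least one intraoperative or postoperative complication up to the visit 1 month after surgery, divided by number of patients operated on. Say in the same place what counts as a complication and how it is graded; CTCAE v5.0 is already the protocol's scale.
2. State in section 9.2.5 that this rate is an exception to the FAS rule, as section 9.3 already does for safety with the SAT Population.
3. Report the surgery-completion rate separately on the FAS, under its own name. The synopsis describes the efficacy set as patients with at least one dose while section 9.2.1 says all enrolled, so confirm which applies.
4. Align section 8.1 and Table 1 footnote 13 with the visit schedule, so that serious surgical complications up to the 1-month visit are recorded in the CRF.
5. Minor: reconcile the downstaging denominator with sections 9.2.5 and 9.2.1. The rate among patients who are node-positive at baseline may be added, since N0 patients cannot be downstaged.

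The cost is a few sentences. No planned confidence interval changes, nor does the sample size or the primary test. One drawback: a rate among operated patients leaves out those who never reach surgery, so it has to be read beside the surgery-completion rate in item 3.
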